As part of this protocol, study participants will participate in one of two cohorts. We will obtain systematic measurements of gait biomechanics (using 3-dimensional motion analyses), corticomotor excitability (using TMS), and walking function (using standard clinical tests of walking performance) through the course of 18 sessions of gait retraining (Cohort 1). In addition, we will investigate how different training strategies and parameters (such as electrical stimulation, fast walking speed, biofeedback) influence within-session and short-term improvements in gait biomechanics and corticomotor excitability (Cohort 2). A total of 35 individuals with stroke and 35 able-bodied individuals will be tested.

In addition to the data-collection described as part of cohort 1 and cohort 2 above, the study will also include 'pilot' or methodology-driven experiments on both able-bodied and stroke participants. These experiments do not include an intervention component and do not fall under the NIH definition of clinical trials. A majority of these pilot experiments will be conducted during the early or planning phase of the study. These pilot or methodological experiments will be utilized to test the measurement properties for the neurophysiological variables measured in the clinical trial, to evaluate short-term effects of the gait training or gait testing conditions, and to establish normative or reference values for able-bodied (as a control comparison for stroke) and stroke survivors (at baseline). The study procedures used for the pilot phase may be similar to those described for cohort 1 and 2, but only a subset of outcomes or tests may be included in the pilot phase, and a shorter duration experiment may be performed (e.g. 1 session instead of multiple evaluation or training sessions). These pilot phase data may contribute to scientific publications that inform our understanding of how methodological parameters such as posture (standing, seated), stimulation intensity, muscle state (active, rest), or timing (inter-stimulus interval between brain and nerve stimulation) influence the neurophysiologic measurements derived during non-invasive stimulation.

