 - H1.* Eighteen sessions (6-8 weeks) of gait training comprising fast treadmill walking and functional electrical stimulation (FastFES) will result in Improvements in gait biomechanics, corticospinal excitability, and walking function.
 - H2.* Improvements in gait biomechanics will precede the improvements in corticospinal excitability and walking function.
 - H3.* Improvements in walking function will be correlated to improvements in corticospinal excitability.
- By utilizing data collected on cohort 2 of subjects who receive different rehabilitation strategies during each training session, we will analyze short-term changes induced by 1-3 sessions of gait retraining to test the following hypothesis:
 - H4.* The magnitude of improvements in gait biomechanics and corticospinal excitability will be greater for gait training sessions that comprise:
 - walking at a faster versus slower speed
 - walking with versus without FES, i.e. Fast versus FastFES
 - walking with FES delivered to two versus one muscle during gait
 - walking with 2 belts going at different speeds or directions versus regular treadmill walking
 - walking with versus without visual bio-feedback or other feedback (e.g. verbal, tactile) about targeted parameters during gait
 - greater dosages (# of walking steps per session) of walking practice
 - combination of 2 strategies versus a single rehabilitation strategy

5. Study design and methods

Research Procedures

Flowchart showing the overview of study procedures.

The overall goal of this protocol is to provide novel insights into the biomechanical and neural mechanisms underlying gait rehabilitation. To achieve this goal, a series of experiments will be performed on young able-bodied individuals as well as stroke survivors. The protocols to be tested and procedures to be used are described in detail here. For all the procedures and sessions described below, all testing procedures will be explained to the subject at the beginning of each testing session. Also,

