Hypotheses testing will be done with a p-value set at 0.05. The outcome variables used for analyses will include peak knee and ankle flexion during walking, propulsive forces during walking, walking speed and endurance, peak and duration of EMG activation during walking, and TMS-derived measures of corticospinal excitability (peak EMG in response to TMS, motor threshold intensity, slope and peak of the TMS-recruitment curve). To test *H1*, for each of the variables, one-way repeated measures ANOVA will be performed to check for differences in the variable after versus before 18 sessions of training. To test *H2*, we will plot the dependent variable versus time (test session number). Using these plots, the time to plateau and the time when the variable first shows a positive within-session change (threshold time) will be determined. One way repeated measures ANOVA will be used to compare the time to plateau and threshold time among 3 variables – peak propulsion, peak TMS muscle response, and over ground walking speed. To test *H3*, a Pearson's correlation will be performed between the change in peak propulsion after training versus change in peak TMS muscle response after training. For the hypothesis involving within-session changes (*H4*), repeated measures ANOVA will be performed to compare the within-session percentage change for each variable between different rehabilitation strategies.

Power Analysis: The current protocol has been powered using the primary outcome measure of paretic propulsive force generation. Based on means and standard deviations from our existing pilot data, for each aim, a sample of 24 subjects will provide 80% power to detect a 4.2% difference in propulsive force between sessions with standard deviation of 6% at a two-sided alpha level of 0.05. After completion, the data from this study will be used to conduct systematic power analysis for other outcome variables, which will be utilized to design a larger-scale future study.

8. Adverse event reporting

We will notify the IRB of any adverse events that occur during the protocol.

10. Device information

Equipment for Motion Analysis and Gait Retraining: A 7-camera system will be used to collect motion analysis data (Vicon, Oxford, UK). Ground reaction forces during treadmill walking will be collected using a treadmill instrumented with two 6-component force platforms under each

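### H2 threshold time counts any positive within-session change as onset, so an outcome that never responds gets an early onset, and outcomes that improve together are ordered by change relative to noise, not by timing

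*Combined protocol and SAP*

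**What the plan says.** H2 (Section 4, Hypotheses of the study) reads: "Improvements in gait biomechanics will precede the improvements in corticospinal excitability and walking function". Section 7 tests it in Cohort 1. Each outcome is plotted against test session number, and two times are read from the plots. One is time to plateau. The other is threshold time: "the time when the variable first shows a positive within-session change (threshold time) will be determined". Then: "One way repeated measures ANOVA will be used to compare the time to plateau and threshold time among 3 variables", the three being peak propulsion, peak TMS muscle response and over ground walking speed. The significance level is 0.05.

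Nothing elsewhere adds a minimum change, an error band, confirmation at a later test, or a rule for a participant who never shows a positive change. The Precis says that pilot experiments will "test the measurement properties for the neurophysiological variables measured in the clinical trial", but Section 7 does not use their results in defining onset.

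The number of tests entering H2 is not stated. Section 5 (Procedures for Gait Training Sessions) has Cohort 1 outcomes taken before, after and at unspecified points during training. The tests around each session are treadmill trials, and excitability is added only for a few sessions.

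**The concern.** Measurement error makes an observed change positive half the time when nothing has happened. A criterion of any change above zero therefore records an onset for outcomes that never respond, and usually records it at once. For outcomes that do respond, the time to the first positive value depends on how large the change is relative to its noise. H2 is a claim about order, and the three outcomes are measured in quite different ways, so there is no reason to expect equal signal-to-noise. The comparison could show an order where none exists, or miss one that does. Time course is the stated purpose of the protocol, so this measure bears directly on it.

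**Working it through.** **Inputs.** The plan states no figure for threshold time, so there is none to reproduce. Two numbers are borrowed from the power statement in Section 7: n = 24, and a 4.2% propulsion difference with SD 6%, giving d = 4.2/6 = 0.7. That is a between-session difference and serves here only as an illustration. (That statement claims 80% power. If 6% is the SD of the paired difference, 24 participants give 90.7%; this does not affect the present point.) The documents give no SD for TMS response or walking speed, so their d values are assumed. The number of tests K is taken as 4, 6 and 18.

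**Formula.** Let d be the true within-session change divided by its SD. With symmetric (normal) error, independent between tests, each test is positive with probability p = Φ(d). The first positive test is geometric: mean 1/p, and probability 1 − (1 − p)^k of being reached by test k.

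**Outcome with no response.** d = 0, so p = 0.5 whatever the SD.
- Reached at test 1: 50%.
- Reached by test 2: 1 − 0.5² = 75%.
- Reached by test 5: 1 − 0.5⁵ = 96.9%.
- Mean: 1/0.5 = 2.0 tests.
- Never reached: 0.5⁴ = 6.3% with 4 tests; 0.5⁶ = 1.6% with 6.

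**Outcomes that respond from the first test.**

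| d | p = Φ(d) | mean threshold (tests) |
|---|---|---|
| 0.2 | 0.579 | 1.73 |
| 0.35 | 0.637 | 1.57 |
| 0.7 | 0.758 | 1.32 |
| 1.0 | 0.841 | 1.19 |

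Two outcomes with the same true change of 4.2 but SDs of 6 and 12 differ by 1.57 − 1.32 = 0.25 of a test, although they start together.

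**Effect on the planned ANOVA.** Simulation: 4,000 trials, n = 24, three independent normal outcomes, repeated measures ANOVA at 0.05, never-positive scored K + 1. There is no lag in any row. Ranges cover K = 4, 6 and 18.

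| d: propulsion / other two | significant, propulsion first |
|---|---|
| none responds | about 1.5% |
| equal d | about 1.5% |
| 0.7 / 0.35 / 0.35 | about 12% |
| 0.8 / 0.1 / 0.3 | 38–41% |
| 1.0 / 0.2 / 0.2 | 50–57% |

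When no outcome responds, the ANOVA rejects in 4–5% of trials even with SDs of 6, 12 and 18, so the less noisy outcome gains nothing.

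**A true lag.** Let propulsion start at session 4 and the others at session 10, with d = 0.7 and 18 tests. Before session 4 there are three tests with no effect, so 1 − 0.5³ = 87.5% of participants have already been given an onset for propulsion. Its mean threshold is 0.5×1 + 0.25×2 + 0.125×3 + 0.125×(3 + 1.32) = 1.92. For the other two it is 2.00. The ANOVA rejects in about 5% of trials, which is its nominal error rate.

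**Would a stricter per-participant cut-off suffice?** Requiring a change above 1.645 SD still gives a non-responder an onset in 26% (6 tests) or 60% (18 tests). Requiring two consecutive exceedances cuts this to 1.1% or 4.0%, but a responder at d = 0.7 is then detected in only 13% or 36%. Crossing time also still depends on signal-to-noise. With a confirmed change from baseline above the minimal detectable change, no lag and d = 1.0/0.2/0.2, propulsion is falsely first in 15–90% of trials when the effect is constant, and in 100% when it accumulates.

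**The case against.** The strongest reply has four parts.

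1. Cohort 1 is described as a case series that informs a later trial. The powered outcome is propulsive force, not timing, and H2 also uses time to plateau. This stands and limits the consequence: threshold time is not the whole H2 test. It does not make the threshold measure valid.

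2. An analyst reading plots might disregard trivial upward movements. That is possible, but no rule says so, and unwritten judgement about onset is no safer when the expected order is known in advance.

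3. The largest error rates need large contrasts in d. This stands. A twofold gap gives about 12%, and equal d gives about 1.5%.

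4. A cut-off at each variable's minimal detectable change is the obvious repair, yet it does not remove the dependence on signal-to-noise. This also stands, and the fix below takes account of it.

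A reader might infer that the less noisy outcome always appears to improve first. The documents do not support that: ordering follows change divided by SD, and only among outcomes that truly improve. Nor do they support saying that propulsion is the favoured outcome in this study, since no SD is given for the other two.

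**Conclusion.** The point holds as a defect in the definition of threshold time. Followed as written, the rule gives a non-responding outcome an onset at test 2.0 on average. It orders simultaneously improving outcomes by change relative to noise, and in the lag case examined it misses the true order. The results for a non-responder need only symmetric error and independence between tests. The ANOVA rates further assume normal, independent outcomes on a common test numbering, and the d values are illustrative. They show how far the rule can mislead and do not forecast the error rate in this study. Time to plateau is a separate measure that is not assessed here, so it does not follow that H2 as a whole is untestable.

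**What to change.** In Section 7, drop the first positive within-session change as the onset criterion and make these changes:

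- Estimate timing from a model of each outcome's whole time course, for example a mixed model or a change-point model. Use the test sessions at which all three outcomes are measured, and state which sessions those are.
- Express timing relative to that outcome's own fitted total change, for example the time to reach 50% of it. The quantity estimated then does not depend on signal-to-noise; its precision still will. State openly that this replaces a within-session change with the course across sessions.
- Compare outcomes by the differences in these times, with participant-level bootstrap confidence intervals.
- Interpret order only for outcomes shown to improve under H1.
- If a per-participant threshold is kept as a description, require a change above that variable's between-session minimal detectable change, confirmed at the next test and calibrated to the number of tests. Treat participants who never reach it as censored. Do not claim order from it alone. Repeat trials within one visit will not supply a between-session value, because they omit day-to-day error such as marker replacement.

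Cost: revised wording and a little more analysis. Intervals may be wide, and an outcome that changes little may have no usable timing estimate.

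### H2 claims an order (biomechanics first), but its only planned test is a three-variable omnibus ANOVA with no direction; a tie could pass as support

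*Combined protocol and SAP*

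**What the plan says.** Section 4 (Hypotheses of the study) states H2 as: "Improvements in gait biomechanics will precede the improvements in corticospinal excitability and walking function".

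Section 7 describes the test. Each variable is plotted against test session number, and then: "Using these plots, the time to plateau and the time when the variable first shows a positive within-session change (threshold time) will be determined". Both times are compared by the procedure "One way repeated measures ANOVA will be used to compare the time to plateau and threshold time among 3 variables", the three being "peak propulsion, peak TMS muscle response, and over ground walking speed". The general rule is "Hypotheses testing will be done with a p-value set at 0.05", and the power paragraph works "at a two-sided alpha level of 0.05".

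Neither section gives a contrast, a pairwise follow-up, a direction or a rule for which pattern of results counts as support for H2. Nothing says which timing measure prevails if the two disagree.

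**The concern.** H2 has two parts, and both must hold: propulsion improves before the TMS response, and propulsion improves before over ground speed. The planned null hypothesis is that all three mean times are equal. Rejecting it shows that at least one time differs from another, not which comes first. One late variable is enough to make F significant while the other two are tied.

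A reader who then looks at the means will see some order, because three sample means are almost never equal. If propulsion happens to be lowest, a significant F together with a favourable-looking order can be reported as biomechanics leading both other domains, although one of the two required differences is only noise. Section 3 calls the magnitude and time course of change the unique aspect of the project, so the time-course claim is prominent in this study.

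**Working it through.** **The plan's own figure.** There is none for H2. The power paragraph says "for each aim, a sample of 24 subjects will provide 80% power" and "to detect a 4.2% difference in propulsive force between sessions with standard deviation of 6" percent, which concerns propulsive force and not these times. Read as a paired t-test (4.2/6 = 0.70, n = 24), those inputs give 90.7% rather than 80%. That is a separate matter and has no bearing here.

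**Inputs.** From Section 7: n = 24, alpha 0.05, three times per person. Assumed: normally distributed times, SD 4 sessions for each, within-person correlation 0.3 or 0.5, means of 6 or 9 sessions.

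**Step 1: the F test does not distinguish the patterns.** With equal SDs and a common correlation, its power depends only on the noncentrality

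λ = n × Σ(mean − grand mean)² / [SD² × (1 − correlation)].

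For means ordered propulsion, TMS, speed:
- H2 true (6, 9, 9): grand mean 8, sum of squares 4 + 1 + 1 = 6.
- Tie (6, 9, 6): grand mean 7, sum of squares 1 + 4 + 1 = 6.
- Reversed (9, 6, 6): grand mean 7, sum of squares 4 + 1 + 1 = 6.

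So λ = 24 × 6 / (16 × 0.7) = 12.9 in all three at correlation 0.3, and 24 × 6 / (16 × 0.5) = 18 at 0.5. On 2 and 46 degrees of freedom, power is about 88% and 97%, whichever pattern is true.

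**Step 2: add a look at the means.** In the tie, propulsion and speed are each equally likely to have the lower sample mean, and TMS is hardly ever lowest. A significant F with propulsion numerically first is therefore expected in about half of the rejections: 88%/2 = 44%, and 97%/2 = 48%.

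**Step 3: require two contrasts.** In the tie, the true difference between speed and propulsion is zero. A two-sided 0.05 paired t-test favours propulsion 2.5% of the time, so requiring both contrasts cannot exceed 2.5% apart from simulation error.

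**Step 4: simulation (20,000 runs per pattern).**

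| Means (propulsion, TMS, speed) | Correlation | F significant | F significant, propulsion mean first | Both contrasts favour propulsion |
|---|---|---|---|---|
| Tie (6, 9, 6) | 0.3 | 88% | 44% | 2.5–2.7% |
| Tie (6, 9, 6) | 0.5 | 97% | 48% | about 2.5% |
| Reversed (9, 6, 6) | 0.3 | 88–89% | 0.0% | 0.0% |
| H2 true (6, 9, 9) | 0.3 | 88% | 88% | 74–75% |

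**Step 5: other assumptions.** A second set (40,000 runs per pattern) used shifts of 0.5 to 1.0 SD, correlations of 0 and 0.5, and propulsion tied with TMS ahead of speed. A significant F with propulsion first occurred in 20 to 50% of runs, and both contrasts succeeded in 2.1 to 2.6%. With H2 true, the two contrasts succeeded in 22 to 85% of runs at correlation 0 and 49 to 99% at correlation 0.5.

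**Step 6: sphericity.** With equal means but SDs of 2, 3 and 6, the uncorrected F rejects in about 6.5 to 7% of runs instead of 5%.

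**The case against.** The strongest reply is that nobody reads an F test blind. The plan plots every variable against session, so the order will be seen. This stands for the reversed order. A reader might infer from the 88 to 89% rejection rate that the plan would often report support for H2 when propulsion is last. The documents do not support that: a significant F with propulsion's mean earliest then occurs in 0.0% of runs. The reply fails for ties, where looking at the means still leaves 44 to 48%.

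Second, pairwise comparisons after a significant F are common practice. If the same two contrasts followed the F, the result would be nearly identical to using them alone: 74.0% against 74.3% when H2 is true, and 2.7% either way in the tie. So it would be too strong to say that the ANOVA has no bearing on H2; unequal mean times are a necessary condition for it. What is missing is the step from unequal to ordered, and the plan does not state it.

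Third, Section 5 describes Cohort 1 as a case series to inform a larger trial, and the power statement concerns propulsive force. No efficacy or safety decision depends on H2. This lowers the severity. It does not remove the point, because Section 4 lists H2 as a hypothesis to be tested and Section 7 prescribes its test.

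**Conclusion.** The point holds: as written, the plan can show that the three times differ but cannot establish that propulsion comes first. That conclusion is one of logic, since F is unchanged when the variable labels are exchanged, and it needs no assumed effect size.

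The size is illustrative. Under the assumed values, the exposure in a tie is about 44 to 48%, against about 2.5 to 2.7% with two required contrasts. The normal model is crude: with mean 6 and SD 4, about 11% of times would fall before session 1 (standard normal probability below (1 − 6)/4 = −1.25). Real times are whole sessions, limited by the length of training, and undefined where no plateau is reached. TMS is optional and has extra exclusions, so fewer than 24 people may have all three times. Sphericity is a minor addition.

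This should be fixed before analysis. It is not a flaw that invalidates Cohort 1, and a reader should not infer that the data to be collected cannot answer H2. They can, if the right comparison is specified.

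**What to change.** In Section 7, base the H2 conclusion on two pre-specified paired contrasts: TMS time minus propulsion time, and speed time minus propulsion time, each at two-sided 0.05. Declare H2 supported on a timing measure only if both are significant with propulsion earlier. Because both are required, no multiplicity adjustment between the two is needed, and a paired contrast makes no sphericity assumption.

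State before analysis whether time to plateau or threshold time decides H2; the other is supportive. Report both lags with 95% confidence intervals for both measures. The omnibus ANOVA may stay as a descriptive first step, with a sphericity correction.

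Cost: wording in Section 7 only, with no new data or participants. In the example (correlation 0.3), the chance of declaring H2 supported when it is true falls from about 88% for the omnibus F to about 75%, though the 88% was never power for an ordering. One-sided 0.05 contrasts would give about 85%, but would depart from the two-sided level in the power statement and double the tie-case ceiling to 5%. One of the two timing measures also becomes supportive only.

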Over 7.7 million people are living with the effects of a stroke and about 700,000 experience a stroke or a recurrence of stroke each year¹. Stroke is the leading cause of adult disability contributing to limitations in activities of daily living¹. More than 50% of stroke survivors have walking dysfunctions and receive gait rehabilitation². Even after rehabilitation, residual gait deficits are prevalent in stroke survivors^{2, 3}. Because gait dysfunction limits community mobility, most stroke survivors perceive improvement in their walking as a critical goal of rehabilitation^{4, 5}. There is consensus in the literature that similar to acute stroke patients, chronic stroke patients can benefit from rehabilitation⁶⁻¹³. Thus, there has recently been renewed interest in the rehabilitation research literature toward the development and improvement of gait retraining interventions^{9, 12-29}.

Post-Stroke Gait Dysfunctions

Normal walking is characterized by smooth progression of steps and symmetry between limbs³⁰. However, stroke results in weakness and inappropriate timing and gradation of contractions in muscles of the extremity affected by the stroke³¹⁻³⁴. Post- gait deficits affect all phases of the gait cycle and all lower extremity joints^{32, 34}. Common swing phase post-stroke gait deficits include reduced flexion at hip, knee, and/or ankle joints^{31, 32, 34, 35}. During the stance phase, decreased contribution of the paretic leg to forward propulsion during paretic terminal stance is a critical post-stroke gait deficit shown to be correlated with hemiparetic severity, walking speed, and gait asymmetry^{36, 37}. These gait deficits can lead to falls, increased energy cost of gait, and decreased endurance^{5, 33, 34, 38}. Also, a slowed self-selected walking speed is one of the hallmarks of post-stroke gait, and greatly limits community participation in individuals post-stroke³⁹.

One goal of recent rehabilitation research has been to maximize the efficacy of post-stroke gait rehabilitation by developing new treatments and improving existing interventions^{12, 16, 17, 40-42}. Recently, treadmill training has emerged as an intervention that can improve walking

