Although previous studies investigated the therapeutic effects gained after 6- to 12-weeks of gait rehabilitation^{2, 8, 9, 14, 15, 17, 24, 41, 43, 44, 53}, no information is available about when or how these performance changes evolve during rehabilitation. Are improvements in gait produced after one treatment session? What are the differences in time course of changes in biomechanical (gait kinematics and kinetics), neural (corticomotor excitability), and functional (walking speed and endurance) variables? Another interesting, important, and unaddressed question critical for designing better rehabilitation interventions is: what strategies can clinicians use to maximize improvements in gait achieved from each rehabilitation session? There is a need to systematically evaluate the differential effects of walking speeds, electrical

stimulation parameters, and biofeedback on gait training outcomes. We posit that investigating the short-term within-session changes with gait training is a more cost-effective method of gaining initial insights into response to novel treatment strategies compared to expensive large scale trials.

Animal studies show that task-specific practice of hundreds of repetitions result in reorganization of cortical motor maps and lasting changes in neural networks⁶⁶. These neuroplastic changes in the nervous system can occur within the span of hours⁶⁷. For instance, a study using an animal model showed that forelimb task training lead to rapid (within an hour) formation of new synapses in the motor cortex, and this synaptic neogenesis lasted long after cessation of training⁶⁷. Similarly, if new cortical connections are activated in post-stroke adults immediately after an intensive gait rehabilitation session, we may observe resultant measurable improvements in specific gait parameters during a session and an increase in corticomotor excitability after a few gait training sessions. Also, an emerging research hypothesis is that neuroplasticity changes may be associated with greater potential for response to rehabilitation^{68, 69}. Neurophysiologic measures derived using a non-invasive technique such as TMS can serve as predictors of a patient's potential for response to rehabilitation, and can guide design of more efficacious rehabilitation interventions.

In summary, there is a gap in rehabilitation literature regarding the time course of and mechanisms underlying post-stroke gait rehabilitation.

4. Objectives

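### H3 is about walking function, but its planned test correlates propulsion, a biomechanical variable, with the TMS response

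*Combined protocol and SAP*

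**What the plan says.** Section 4 (Hypotheses of the study) states H3 for Cohort 1, which receives 18 FastFES sessions: "Improvements in walking function will be correlated to improvements in corticospinal excitability". Section 7 (Statistical analysis) tests it by Pearson's method: the "correlation will be performed between the change in peak propulsion after training versus change in peak TMS muscle response after training".

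Elsewhere the protocol says which variables belong to which domain:

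- Section 2 (Precis/Abstract) lists three kinds of measurement: "gait biomechanics (using 3-dimensional motion analyses), corticomotor excitability (using TMS), and walking function (using standard clinical tests of walking performance").
- Section 3, on the need to understand time course and mechanisms, separates "biomechanical (gait kinematics and kinetics), neural (corticomotor excitability), and functional (walking speed and endurance) variables".
- H2 in Section 4 reads "Improvements in gait biomechanics will precede the improvements in corticospinal excitability and walking function". Its test in Section 7 compares "peak propulsion, peak TMS muscle response, and over ground walking speed", one variable for each domain.
- The outcome list in Section 7 includes "propulsive forces during walking, walking speed and endurance" as separate items.

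**The concern.** H3 is the only hypothesis that links neural change to functional change across the 18 sessions, which is central to a study of cortical and spinal correlates of gait rehabilitation. Its test uses a variable that the protocol files under biomechanics.

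If Section 7 is followed, a significant propulsion-TMS correlation would be reported as support for H3 when it shows a link between biomechanics and excitability. A null result would say little about walking function. An analyst who noticed the gap after seeing the data and substituted walking speed would be running an unplanned analysis.

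**Working it through.** **1. Hypothesis against test.**

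| | First variable | Second variable |
|---|---|---|
| H3 as stated (Section 4) | change in walking function | change in corticospinal excitability |
| H3 as tested (Section 7) | change in peak propulsion | change in peak TMS muscle response |

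The second column matches, because peak TMS response is one of the excitability measures listed in Section 7. The first does not.

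**2. Where propulsion belongs.** Propulsion comes from ground reaction forces, which Section 5 collects under motion analysis. Forces are kinetics, and Section 3 calls kinetics biomechanical. Self-selected over ground speed and 6-minute walk distance are in the Section 5 procedure for clinical assessment of walking function. H2 requires the two domains to be distinct, since one is predicted to improve before the other. The H2 test uses propulsion and over ground speed side by side, so using propulsion for function in the H3 test conflicts with it.

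**3. Is H3 tested elsewhere?** No. Section 7 lists speed and endurance as outcomes and analyses them under H1, and speed again under H2. No correlation of either with a TMS change is planned.

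**4. Could propulsion stand in for function?** The protocol gives no figure for the H3 correlation. Its only sample-size statement (24 subjects, 4.2% difference in propulsive force, SD 6%, two-sided 0.05, 80% power) concerns a mean difference. I use n = 24 from it only for illustration. The correlations below are assumptions.

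Let *a* be the true speed-TMS correlation and *b* the propulsion-speed correlation, both for change scores. The propulsion-TMS correlation must lie within ab ± √[(1 − a²)(1 − b²)]. If propulsion relates to TMS only through speed, it equals ab. Power at n = 24, two-sided 0.05, is approximately Φ(atanh(r)·√21 − 1.96).

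Take a = 0.54. Power for a direct test is Φ(0.604 × 4.583 − 1.96) = Φ(0.81) = 0.79, or about 80%. For b = 0.5, ab = 0.27 and the half-width is √(0.708 × 0.75) = 0.729. The bounds are −0.46 and 1.00. Power at r = 0.27 is Φ(0.277 × 4.583 − 1.96) = Φ(−0.69) = 0.245.

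| Assumed b | Possible propulsion-TMS correlation | ab | Power at ab, n = 24 |
|---|---|---|---|
| 0.5 | −0.46 to 1.00 | 0.27 | 0.245 |
| 0.7 | −0.22 to 0.98 | 0.54 × 0.7 = 0.378 | Φ(0.398 × 4.583 − 1.96) = 0.45 |
| 0.9 | 0.12 to 0.85 | 0.54 × 0.9 = 0.486 | Φ(0.531 × 4.583 − 1.96) = 0.68 |

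The bounds are symmetric in the two TMS correlations. An observed propulsion-TMS correlation of 0.54 would leave the speed-TMS correlation in the same ranges. At b = 0.5 or 0.7 even its sign is open.

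**5. What the correct test can detect.** The smallest correlation with 80% power is tanh[(1.96 + 0.842)/√(n − 3)]. That is 0.535 at n = 25 (Cohort 1 in Section 4), 0.545 at n = 24, and 0.567 at n = 22 (25 less about 10% withdrawal).

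**The case against.** The mismatch itself is not seriously disputable, but several points can be made against its weight.

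- **Usage is not uniform.** The Section 2 paragraph on existing MRI scans runs walking function and biomechanics together. That concerns a preliminary analysis in an able-bodied subset, and it does not override the definitions and H2 test that govern Cohort 1.
- **Propulsion is a relevant proxy.** Section 3 says that paretic propulsion is "shown to be correlated with hemiparetic severity, walking speed, and gait asymmetry". This stands to a degree: the planned test is indirect rather than irrelevant. But no coefficient is given, and nothing is said about whether changes in the two move together.
- **Propulsion is the primary outcome.** True, and it explains the power calculation. It does not make propulsion a measure of function. It does leave open that the slip is in H3's wording rather than in the test.
- **The illustration rests on assumptions.** Also true. The intervals are mathematical limits rather than plausible ranges, and at b = 0.9 the sign is settled. The finding does not depend on them.
- **A null result would be weak even from the correct test.** At n = 24 its power is about 29% for r = 0.3 and 49% for r = 0.4. This stands, and is a separate limitation.
- **Cohort 1 is a case series meant to inform a larger trial, and H3 is not the powered comparison.** This limits the damage to H3, which still has no valid planned test.

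**Conclusion.** The concern holds. As written, Section 7 contains no test of H3: the planned correlation addresses biomechanics and excitability, and its result can neither confirm nor refute a claim about walking function. This follows from the protocol's own definitions and needs no assumed number.

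The possible loss of power, from about 80% to between 25% and 68%, is illustrative. It assumes 24 pairs, a true speed-TMS correlation of 0.54, propulsion-speed correlations of 0.5 to 0.9, and a link that runs only through speed.

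The fault is confined to H3. H1, H2, H4 and the power calculation for propulsion are unaffected. It should be corrected before analysis, because one of the stated hypotheses otherwise has no matching test and the repair is small.

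**What to change.** Replace the H3 sentence in Section 7. Test H3 as the Pearson correlation between the change in over ground self-selected walking speed and the change in peak TMS muscle response, before versus after the 18 sessions. Use 6-minute walk distance as a secondary functional measure. Keep the propulsion-TMS correlation as a labelled exploratory analysis.

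If the sponsor did intend biomechanics, H3 in Section 4 should be reworded instead. That restores consistency but leaves the function-excitability question without a planned test. Whichever is chosen, it should be fixed before the change scores are examined.

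The cost is one sentence. H2 already needs over ground speed and peak TMS response in Cohort 1, and endurance is a listed outcome, so no new procedure is required. Because Section 5 words the clinical tests permissively, makes TMS optional and allows clinical testing to be skipped in able-bodied subjects, the new sentence should also say which Cohort 1 participants enter the analysis and require both measures before and after training. The report should give the number of complete pairs and a confidence interval for the correlation.
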